#### Secondary endpoints

Disease-free survival time (in months): Disease-free survival curves were plotted using the Kaplan-Meier method; differences in the risk of disease-free survival between the two groups were assessed using the Log-Rank test with 95% confidence intervals; multivariate analyses were performed using the Cox proportional risk model to assess the effect of subgrouping factors (surgical procedure) and other prognostic factors on the risk of disease-free survival, with 95% confidence intervals for each factor. A multivariate analysis using the Cox proportional risk model was performed to assess the effect of grouping factors (surgical modality) and other prognostic factors on the risk of disease-free survival with 95% confidence intervals for each factor.

- Surgical evaluation indicators.
- Surgical time (unit: minutes), intraoperative bleeding (unit: ml), intraoperative blood transfusion (unit: ml): all quantitative data not conforming to normal distribution, calculate the median, 25% quartile, 75% quartile, the minimum value, the maximum value, and analyze the difference between the two groups by using the rank sum test.
- Incidence of intraoperative accidents: count data, using chi-square test to analyze the difference between the two groups.
- Lymph node dissection: the total number of lymph node dissection (unit: one) and the number of lymph node dissection at each station (unit: one) were non-normally distributed measurements, and the difference between the two groups was analyzed using the rank-sum test; the number of stations of lymph node dissection (intrapulmonary, hilar, and ipsilateral mediastinal lymph nodes) was count data, and the difference between the two groups was analyzed using the chi-square test. Differences between the two groups were analyzed using the chi-square test.
- Tumor R0 resection rate: count data, using the chi-square test to analyze the difference between the two groups.
- Perioperative, 30-day, and 90-day complication rates, and mortality rates: were count data, and differences between the two groups were analyzed using the chi-square test.
- Quality of Survival and Cardiorespiratory Function Evaluation at Admission, Discharge, 30 Days, and 90 Days
- Quality of Life Score SF-36 Scale: Percentage, as a non-normally distributed measure, use rank sum test to analyze the difference between the two groups.
- Resting oxygen saturation (in percent): a non-normally distributed measure, differences between the two groups were analyzed using the rank-sum test.
- 

Lung function: Tidal volume, Vital capacity, Forced vital capacity, Forced Expiratory Volume In 1s, all in ml: were normally distributed measures and analyzed using the student The differences between the two groups were analyzed using the student-t test with 95% confidence intervals.

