#### Secondary study endpoints

- Overall survival (OS, unit:month)
- Disease-free survival (DFS, unit: month)
- Surgical Evaluation Indicators.
  - Surgical time (unit: minutes), intraoperative bleeding (unit: ml), intraoperative blood transfusion (unit: ml)
  - Incidence of intraoperative accidents
  - Lymph node dissection: total number of lymph node dissection (unit: one), number of lymph node dissection stations (intrapulmonary,hilar and ipsilateral

mediastinal lymph nodes), and the number of lymph nodes cleared at each station (unit: one).

- Perioperative, 30-day, 90-day complication rates, mortality rates
- Quality of Survival and Pulmonary Function Evaluation at Admission, Discharge, 30 Days, and 90 Days
  - Quality of Life Score: Scored using the short form-36 (SF-36) and recorded on a 100-point scale.
  - Resting oxygen saturation (unit: percentage)
  - Lung function: Tidal volume, Vital capacity, Forced vital capacity, first second vital capacity.
  - Tidal volume, Vital capacity, Forced Expiratory Volume In 1s, all in ml.

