### **5.3 Determination of sample size**

This study is a prospective observational clinical study, and the purpose of the study is to evaluate the feasibility and long-term outcome of pneumonectomy to lobectomy after neoadjuvant or induction chemoimmunotherapy for locally progressive non-small cell lung cancer. Due to the lack of previous reference data, the sample size was not calculated based on hypothesis testing, and 50 patients were enrolled.

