### **6.4 Methods of Study Subject Allocation**

This study is a single-arm clinical trial and does not involve the allocation of study subjects to the enrollment group.

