## 10. Statistical analysis

### 10.1 General methodology

All statistical analyses were performed using R software, and hypothesis tests were standardized using two-sided tests, giving the test statistic and its corresponding p-value.  $p<0.05$  was considered statistically significant, and 95% confidence intervals were set as required.

Statistical description: All indicators are described according to their nature. Qualitative indicators are expressed as frequencies and percentages of categories; metrics provide the number of cases, mean, standard deviation, median, minimum and maximum values.

Statistical inference: For overall survival time and disease-free survival time, overall survival curves and disease-free survival curves were plotted using the Kaplan-Meier method; risk differences between survival and disease-free survival were assessed using the Log-Rank test; multivariate analyses were performed using the Cox proportional risk model to assess the effect of subgrouping (surgical modality) and other prognostic factors on survival and disease-free survival. survival and disease-free survival. The t-test was used for measures that were normally distributed, and the rank-sum test was used for measures that were not normally distributed; the chi-square test was used for between-group comparisons of count data, and the Fisher exact probability method was used when necessary.

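### Section 10.2 summarises intraoperative transfusion only as a skewed volume in ml; if fewer than about a quarter of each group are transfused, the median and both quartiles are 0 ml, and no planned figure gives the number transfused

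*Protocol*

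**What the plan says.** Section 5.2 of the protocol lists the endpoint among the surgical evaluation indicators, as a volume only: "intraoperative blood transfusion (unit: ml". It has no yes/no transfusion endpoint.

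Section 10.2 (Secondary endpoints) places it in one bullet with operating time and intraoperative bleeding and prescribes: "intraoperative blood transfusion (unit: ml): all quantitative data not conforming to normal distribution, calculate the median, 25% quartile, 75% quartile". The sentence continues: "the minimum value, the maximum value, and analyze the difference between the two groups by using the rank sum test".

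Section 10.1 has a general rule for quantitative measures: "metrics provide the number of cases, mean, standard deviation, median, minimum and maximum values". Read together with 10.2, this adds the number of cases, the mean and the SD.

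Neither section plans a count or percentage of patients transfused, and no expected transfusion rate appears anywhere in the protocol.

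**The concern.** Operating time is positive for everyone operated on, so a median with quartiles describes it well. Transfusion volume is a mixture: a block of exact zeros (patients not transfused) and some positive volumes (patients transfused). It answers two questions, how many patients needed blood and how much they received, and a single set of quartiles over all patients separates neither.

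If transfusion is uncommon, the table would read 0 (0–0) ml in each group. A small p-value beside that line would be hard to interpret, and a large one would leave the reader with no idea of the rate or its precision. The protocol's case for the smaller resection rests partly on perioperative safety (sections 2.2 and 2.4.2), so the proportion transfused is a natural figure to want. Section 10.2 already treats intraoperative accidents and complications as count data.

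**Working it through.** **Inputs.** From the protocol: 50 patients, with "the sample size was not calculated based on hypothesis testing, and 50 patients were enrolled"; the summaries in 10.1 and 10.2; two-sided tests. Assumed, because the protocol gives none: the transfusion rate (5% to 24%), the group sizes (35/15, 25/25, 40/10) and, where a volume is needed, 400 ml per transfused patient unless stated. The protocol has no figure of its own to reproduce.

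**1. When is the 75% quartile 0 ml?** With R's default quartile, the 75% point of n ordered values lies at position 1 + 0.75(n − 1). For n = 35 this is 26.5, so the 26th and 27th values must both be zero. That needs at least 27 zeros, so at most 8 transfused. In the same way:

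| Group size | Most transfused with 75% quartile = 0 |
|---|---|
| 10 | 2 |
| 15 | 3 |
| 25 | 6 |
| 35 | 8 |
| 40 | 9 |

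Whenever the 75% quartile is 0, the 25% quartile and the median are 0 too.

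**2. How likely is that?** For one group it is the binomial probability P(X ≤ k), with k from the table. For both groups at the same rate, multiply.

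| Assumed rate | n = 35 | n = 15 | Both, 35/15 | Both, 25/25 | Both, 40/10 |
|---|---|---|---|---|---|
| 5% | 1.00 | 0.99 | 0.99 | 1.00 | 0.99 |
| 10% | 0.99 | 0.94 | 0.94 | 0.98 | 0.93 |
| 15% | 0.93 | 0.82 | 0.77 | 0.87 | 0.77 |
| 20% | 0.75 | 0.65 | 0.48 | 0.61 | 0.50 |
| 24% | 0.53 | 0.50 | 0.26 | 0.37 | 0.28 |

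All-zero quartiles are very likely at 10% or below and about an even chance at 20%.

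**3. The condition applies within each group.** With 4/40 v 4/10 transfused, 8/50 = 16% overall, the 75% quartile is 0 v 400 ml. A low overall rate is therefore not enough.

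**4. Do the minimum and maximum supply the count?** Take 1/25 transfused (800 ml) against 6/25 transfused (one with 800 ml, five with 200 ml). The minimum, quartiles and maximum are 0/0/0/0/800 ml in both groups, yet the proportions are 4% and 24%. The means differ, 800/25 = 32 ml v (800 + 5 × 200)/25 = 72 ml. But a mean mixes frequency with volume: 32 ml is equally four of 25 patients at 200 ml each.

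**5. Does the rank-sum test see the difference?** Yes. With all quartiles 0 in both groups and 400 ml per transfused patient (tie-corrected rank-sum test):

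| Transfused | Rank-sum p | Fisher p |
|---|---|---|
| 0/25 v 6/25 | 0.010 | 0.022 |
| 0/35 v 3/15 | 0.007 | 0.023 |
| 2/35 v 3/15 | 0.13 | 0.15 |

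The test follows the share of non-zero values, but it yields a p-value without an estimate.

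**6. What the proportion adds.** For 2/35 v 3/15 the 10.2 quartile summary is 0 (0–0) ml in both groups. The proportions are 5.7% (Wilson 95% CI 1.6 to 18.6) and 20.0% (7.0 to 45.2), a difference of 14.3 points. The Newcombe limits are

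- lower: 14.3 − √[(20.0 − 7.0)² + (18.6 − 5.7)²] = 14.3 − 18.3 = −4.0
- upper: 14.3 + √[(45.2 − 20.0)² + (5.7 − 1.6)²] = 14.3 + 25.5 = 39.8

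The interval is wide and includes zero, but it tells the reader the direction, the size and how little 50 patients can settle.

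**The case against.** A reader might infer that the planned analysis says nothing about transfusion, or could not show a difference if there were one. The documents do not support that. Section 10.2 includes the minimum and maximum, section 10.1 adds the mean and SD, and the rank-sum test responds to the proportion transfused even when every quartile is zero (step 5). In those examples its p-values are no larger than Fisher's, so the fix does not make detection easier.

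Three further objections deserve weight. First, the zero quartiles depend on a rate that the protocol does not give. Section 7.1.1 allows sleeve resection with pulmonary angioplasty in patients first thought to need pneumonectomy, so a low rate cannot be taken for granted. This stands, and it makes that part of the point conditional. Second, median, quartiles and a rank test are a conventional choice for a skewed volume, and an extra row with n (%) is the kind of detail often left to a SAP or table shells. This stands in part: the protocol is not silent here but prescribes a specific summary, and a SAP that followed 10.2 would carry it forward. Third, the count can be derived at any time from the recorded ml, and nothing forbids reporting it. That is true, and it is why the change is nearly free.

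The same sentence of 10.2 compares two groups, although section 6.4 says: "This study is a single-arm clinical trial and does not involve the allocation of study subjects to the enrollment group". That is a larger but separate question. A proportion transfused with its interval is useful even with no comparison.

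**Conclusion.** The point holds as a minor one. Section 10.2 fixes a summary that suits operating time but fits badly a volume that is zero for every untransfused patient. If fewer than about a quarter of each group are transfused, the median and both quartiles are 0 ml. At equal rates and the three assumed splits, the chance of that in both groups is 0.93 to 0.98 at a 10% rate and 0.48 to 0.61 at 20%. Whatever the rate, none of the planned figures gives the number transfused, or an estimate of the transfusion rate with an interval.

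It goes no further than that. The endpoint is not left without information, the planned test can detect a difference, and nothing in the protocol rules out reporting the count. The rates, group sizes and volumes used here are assumptions. The primary endpoint and the trial's conduct are not affected.

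**What to change.** In section 10.2, take transfusion out of the shared bullet and give it its own sentence:

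- report the number and percentage of patients transfused, with a 95% CI;
- if groups by surgical procedure are compared, add the difference in proportions with a 95% CI;
- describe the volume in ml among those transfused only (median, quartiles, range).

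The rank-sum test on all patients may stay as a supplement. Median and quartiles remain as they are for operating time and blood loss. The cost is one sentence in the protocol and one extra table row. Transfused yes/no follows from whether the recorded ml is above zero, so no new data are needed.

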#### Secondary study endpoints

- 1) Lymph node dissection: Record the total number of lymph node dissection, the number of stations of lymph node dissection, and the number of lymph node dissection at each station during the operation, and evaluate them according to the pathologic results.
- 2) Perioperative indicators: Record the duration of surgery, intraoperative bleeding, the incidence of intraoperative accidents, evaluated by surgical records and perioperative clinical manifestations, laboratory tests, physical examination;
- 3) Postoperative short-term efficacy indicators: record the length of postoperative hospitalization (days), survival within 30 days after surgery, and evaluate through postoperative follow-up;
- 4) Perioperative complication rate: Evaluated by clinical manifestations, laboratory tests, and physical examination.
- 5) 3-year disease-free survival rate: defined as the proportion of patients without tumor recurrence or metastasis 3 years after surgery, evaluated by postoperative follow-up.
- 6) 3-year overall survival rate: defined as the proportion of patients who are still alive 3 years after surgery, and evaluated by postoperative follow-up.

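### Section 10.2 tests the number of lymph-node stations, an ordered number per patient, with chi-square, which discards the order and loses power; the node counts in the same bullet get rank-sum

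*Protocol*

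**What the plan says.** Section 5.2 of the Protocol lists three lymph-node items as secondary endpoints: total nodes, the "number of lymph node dissection stations (intrapulmonary,hilar and ipsilateral" mediastinal regions), and nodes at each station. Section 9.1 has all three recorded, including "the number of stations of lymph node dissection, and the number of lymph node dissection at each station during the operation". Each is a whole number per patient.

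Section 10.2 then splits them. Total nodes and nodes at each station "were non-normally distributed measurements, and the difference between the two groups was analyzed using the rank-sum test". The number of stations "was count data, and the difference between the two groups was analyzed using the chi-square test". Elsewhere in section 10.2 the count-data label is used for yes/no rates, for example "Tumor R0 resection rate: count data, using the chi-square test to analyze the difference between the two groups", and likewise for intraoperative accidents, complications and mortality.

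Section 10.1 sets the general rules: "the rank-sum test was used for measures that were not normally distributed"; chi-square for count data, where "the Fisher exact probability method was used when necessary"; and "hypothesis tests were standardized using two-sided tests" at the 0.05 level. No cut-point or set of categories is given that would turn the number of stations into a proportion.

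**The concern.** The label appears to have decided the test. In this protocol it means frequencies of categories, yet the number of stations is a numeric variable of the same kind as the number of nodes. Pearson chi-square treats 4, 5, 6 and 7 stations as unrelated categories, so shuffling those values leaves the statistic unchanged. It also spends a degree of freedom on each extra distinct value. A consistent shift towards fewer stations in one group is the pattern of interest, and the test is not directed at it.

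At stake is the sensitivity of one measure of how complete the nodal dissection was, which bears on whether the smaller operation is oncologically sound. The protocol fixes this test itself, so it is not a detail left for a later analysis plan.

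**Working it through.** **Figure to reproduce.** None. The protocol gives no power, effect size or sample-size calculation for this endpoint.

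**Inputs from the protocol.** 50 patients, not based on a hypothesis test (section 5.3); two-sided 0.05 (section 10.1); single arm with no allocation (section 6.4). Surgical modality is the grouping factor in sections 10.1 and 10.2, but the two groups are neither defined nor sized.

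**Assumptions, not in the protocol.** Group splits of 25/25, 35/15 and 40/10; the distributions stated below.

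**Step 1: sparse cells.** For a 2 × k table of group by number of stations, E = (row total × column total) / 50, X² = Σ(O − E)²/E, with k − 1 degrees of freedom. The expected counts in the smaller group add up to its size, so the number of its cells that can reach 5 is at most size / 5:
- 25/25: 25 / 5 = 5 values
- 35/15: 15 / 5 = 3 values
- 40/10: 10 / 5 = 2 values

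In simulation with rounded normal station counts (SD 1.0 to 2.0), about 5 to 10 distinct values occur, and on average 51% to 89% of expected counts are below 5.

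**Step 2: power if individual stations are counted.** Assumed mean 6 and SD 1.7, rounded and clipped to 1–11; 4,000 simulated trials per setting.

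| Split | True difference | Chi-square | Rank-sum | Loss (points) |
|---|---|---|---|---|
| 35/15 | 1 station | 13.6% | 44.0% | 30.4 |
| 35/15 | 1.5 stations | 32.8% | 77.8% | 45.0 |
| 25/25 | 1 station | 13.6% | 49.7% | 36.1 |

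A separate repeat of the 35/15 rows gave 14% versus 43% and 31% versus 76%.

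**Step 3: other assumptions.** SD 1.0, 1.5 or 2.0, all three splits, true shift of 0.8 SD, 2,000 trials each: chi-square 20–40%, rank-sum 55–77%. The smallest loss is 54.6 − 31.1 = 23.5 points (40/10, SD 1.0); the largest is 76.6 − 22.2 = 54.4 points (25/25, SD 2.0).

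**Step 4: Fisher fallback.** SD 1.5, shift 0.8 SD, 1,000 trials, Fisher test extended to the 2 × k table:

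| Split | Chi-square | Fisher | Rank-sum |
|---|---|---|---|
| 25/25 | 29.8% | 36.6% | 76.8% |
| 35/15 | 29.1% | 33.1% | 72.2% |
| 40/10 | 26.8% | 27.1% | 55.5% |

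**Step 5: no true difference.** In the Step 3 settings chi-square rejects in 2.4–5.1% of trials and rank-sum in 4.1–6.0%. The Monte Carlo standard error is √(0.05 × 0.95 / 2000) = 0.5 points.

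**Step 6: power if only three regions are counted.** Nine settings (three pairs of assumed three-level distributions, three splits). The largest loss is 65.4 − 52.7 = 12.7 points (25/25); the smallest is 51.1 − 46.9 = 4.2 points (40/10).

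**The case against.** The strongest case against the point is that it is small and partly conditional.

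- **The reading of stations.** Sections 5.2 and 10.2 follow the word with only three regions. On that reading a categorical test is less odd and the loss is 4 to 13 points. This stands as a limit on size. Three ordered levels are still ordered, and rank-sum still does better in every setting tried.
- **Sparse tables are provided for.** Section 10.1 allows Fisher's exact test. That deals with the validity of the p-value, but the test is equally blind to order and recovers little power (Step 4).
- **Other variables would show a shortfall.** An undissected station contributes no nodes, and total nodes and nodes per station already get rank-sum. Descriptive reporting does not depend on the test. This stands.
- **The two groups are not defined.** In a single-arm study with no allocation this is the larger problem, and removing all group tests would remove this line too. But surgical modality is the named grouping factor and section 7.1.1 allows both pneumonectomy and lobectomy. If the groups are defined and the tests kept, this line remains wrong.

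A reader might infer that chi-square would cause a real shortfall in nodal dissection to be missed, and that rank-sum would find it. The figures do not support that: at a 1-station difference and 35/15, rank-sum also misses it more often than not (44% power).

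**Conclusion.** The point holds as a wrong test stated for one secondary endpoint, and as an inconsistency within one bullet and with section 10.1. The consequence is lost power.

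The size depends on what is counted. For individual stations, under the assumptions in Steps 2 and 3, the loss is roughly 24 to 54 points. For three regions it is about 4 to 13. The distributions and group sizes behind both ranges are assumed, so neither can be read as a property of this trial.

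Two further inferences are not supported. Sparse cells might suggest too many false-positive results, but the rejection rate with no true difference stays near or below 5%. A fault in the test plan might suggest doubt about the main result, but the primary endpoint does not use this test, and the sample size was not set by power for any endpoint. This is a minor correction.

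**What to change.** In section 10.2, move the number of stations into the first half of the lymph-node bullet, with the node counts, as a measure that is not normally distributed. Report its median, quartiles, minimum and maximum overall, the summary that section 10.2 already gives for operating time, bleeding and transfusion. If any comparison by operation is kept, replace chi-square with the rank-sum test for this item. State whether individual stations or the three regions are counted. If a proportion is wanted instead, name the cut-point in advance.

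The cost is one line of wording. No extra data are needed, since section 9.1 already has the number recorded.

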## **7. Research interventions**

### **7.1 Giving the research intervention**

#### **7.1.1 Description of the research intervention**

After the patients were enrolled in the group, further relevant examinations (bronchoscopy, chest enhanced CT, PET-CT (optional), cranial MR, cardiac ultrasound, pulmonary function, electrocardiogram, and blood test) were completed, contraindications to surgery were ruled out, and they were evaluated to receive neoadjuvant/induced chemo-immunotherapy after multidisciplinary discussion (thoracic surgery, respiratory medicine, pathology). After completion of treatment, the patient is reassessed and discussed multidisciplinary for surgical feasibility. Open or minimally invasive (thoracoscopic-assisted, robotic-assisted) radical lung cancer surgery with systemic lymph node dissection is performed, including

pneumonectomy, lobectomy, combined lobectomy, and sleeve lobectomy (with or without pulmonary angioplasty/sleeve). Based on the surgical pathology and guidelines, the postoperative adjuvant treatment and follow-up plan was individualized after multidisciplinary discussion.

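### Section 10.2 names the Student t-test for lung function between groups apparently formed by the operation performed; if those groups differ in both size and spread, a pooled test misstates its p-values and intervals, and naming Welch's test would avoid this cheaply.

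*Protocol*

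**What the plan says.** Section 10.2 (Secondary endpoints) takes tidal volume, vital capacity, forced vital capacity and forced expiratory volume in one second, all in ml. It states that they "were normally distributed measures and analyzed using the student" test, and then: "The differences between the two groups were analyzed using the student-t test with 95% confidence intervals". The assessments are at admission, discharge, 30 days and 90 days.

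Section 10.1 gives the general rule: "The t-test was used for measures that were normally distributed, and the rank-sum test was used for measures that were not normally distributed". It adds that "hypothesis tests were standardized using two-sided tests", that p<0.05 "was considered statistically significant, and 95% confidence intervals were set as required", and that "All statistical analyses were performed using R software". No R function or option is named. Normality is asserted in advance. Neither section mentions equal variances, pooling or Welch's test.

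The lung-function item does not define its two groups. The only grouping factor that sections 10.1 and 10.2 name, for the Cox models, is the surgical modality or procedure. Section 6.4 says that there is no allocation, and section 7.1.1 lists the possible operations as "pneumonectomy, lobectomy, combined lobectomy, and sleeve lobectomy (with or without pulmonary angioplasty/sleeve)". Section 5.3 sets 50 patients without a calculation.

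**The concern.** Student's two-sample t-test has a second condition besides normality: either the two variances are equal, or the groups are of equal size. The protocol asserts normality and is silent on the rest.

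The design gives no reason to expect equal sizes. Nobody is allocated to an operation. The purpose is to convert planned pneumonectomies to lobectomies, so the more often this succeeds, the smaller any pneumonectomy group becomes. Nor is there reason to rely on equal spread after surgery, since the groups would differ in how much lung was removed.

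At stake are the error rate of the tests and the coverage of the intervals for four measures at three postoperative times. If the smaller group is the more variable one, differences are declared too often and intervals are too narrow. If it is the less variable one, tests are too cautious and intervals too wide.

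**Working it through.** The protocol states no power, effect size, SD or group size for lung function, so there is no figure of its own to reproduce. The check is whether the mechanism is real and how large it could be.

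**Inputs from the protocol.** Total N = 50 (section 5.3); two-sided 5% tests and 95% intervals (section 10.1); Student t-test (section 10.2).

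**Assumptions.** Group splits from 25/25 to 45/5; ratio *r* = SD of the smaller group divided by SD of the larger group, from 0.5 to 2; normal data; all 50 patients operated on and measured.

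**Step 1: standard errors.** Set the larger group's SD to 1, with sizes n1 (larger) and n2 (smaller).

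- Pooled: √{[(n1−1) + (n2−1)r²]/(n1+n2−2) × (1/n1 + 1/n2)}
- True: √(1/n1 + r²/n2)

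At 40 v 10:

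- r = 2: pooled √[(39 + 36)/48 × 0.125] = 0.442; true √(0.025 + 0.400) = 0.652; quotient 0.68 (interval too narrow).
- r = 0.5: pooled √[(39 + 2.25)/48 × 0.125] = 0.328; true √(0.025 + 0.025) = 0.224; quotient 1.47 (interval too wide).
- r = 1, or n1 = n2 with any r: quotient 1.

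**Step 2: type I error.** Simulation with equal means, 100,000 data sets per cell (Monte Carlo standard error near 5%: √(0.05 × 0.95/100,000) = 0.07 percentage points). Entries are rejection rates of the pooled test in %; the last column is the range of Welch's test over all ratios run.

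| Split | r = 0.5 | 0.67 | 1 | 1.25 | 1.5 | 2 | Welch |
|---|---|---|---|---|---|---|---|
| 25/25 | 5.2 | 5.0 | 5.0 | 5.0 | 5.1 | 5.2 | 4.8–5.0 |
| 30/20 | 2.9 | 3.4 | 5.1 | 6.0 | 6.8 | 8.4 | 4.9–5.1 |
| 35/15 | 1.3 | 2.3 | 5.1 | 7.2 | 9.3 | 12.7 | 5.0–5.2 |
| 40/10 | 0.5 | 1.5 | 5.0 | 8.7 | 12.3 | 18.2 | 5.1–5.2 |
| 45/5 | 0.1 | 0.8 | 4.9 | 10.2 | 15.3 | 25.1 | 5.3–5.8 |

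The interval is the test turned round, so its coverage is 100% minus the entry: at 40 v 10, 100 − 18.2 = 81.8% for r = 2 and 100 − 0.5 = 99.5% for r = 0.5, against a stated 95%.

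**Step 3: power at 40 v 10.** True difference of 1 SD of the larger group.

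- Equal SDs: pooled about 79%, Welch about 75%. The exact pooled value agrees: noncentrality 1/√0.125 = 2.83 on 48 degrees of freedom gives 79.1%.
- r = 0.67: pooled about 89%, Welch about 95%.

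The column r = 1 and the row 25/25 show that both conditions, unequal sizes and unequal SDs, are needed before anything goes wrong.

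**The case against.** The strongest reply is that the protocol never says equal-variance or pooled. That is read from the name of the test. Section 10.1 says only t-test and leaves the analysis to R, whose standard two-sample t-test uses the Welch form unless told otherwise (general knowledge of the software, not stated in the protocol). The variance option is a detail often left to a statistical analysis plan. This stands in part: a reader might infer that the protocol deliberately commits to equal variances, and the text does not go that far. But section 10.2 does name a specific test, whose usual meaning is the pooled one. If the name is meant loosely, two analysts could report different intervals from the same data. The same edit settles both readings.

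Second, a reader might infer that unequal spread is likely, or that the stated intervals and tests already fail. The documents do not support that. They contain no lung-function SDs and no group sizes, so neither the presence nor the direction of an error can be established.

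Third, the argument from the extent of resection does not reach the admission measurement, taken before any operation. That is correct, and the point is limited to discharge, 30 days and 90 days.

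Fourth, the larger weakness in the same sentence is that a single-arm study compares two groups that it never defines, with several operations possible. That is also correct. It does not make the variance question irrelevant, because any comparison of means between operations that is kept needs a valid standard error.

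**Conclusion.** The point holds as a conditional one. The named test, in its usual sense, relies on equal spread or equal group sizes; the protocol supports neither, and unequal sizes are plausible from the design. Under the assumed 40 v 10 split and SD ratios of 0.5 to 2, the error rate runs from about 0.5% to about 18%, against about 5% for Welch. At a milder 30 v 20 split the range is 2.9% to 8.4%. With equal SDs or equal sizes there is no problem.

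These figures rest wholly on assumed splits and SD ratios. The analysis is secondary, and the sample size was not based on hypothesis testing, so no primary conclusion turns on it. This is a cheap improvement, not the correction of a proven error.

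**What to change.** If the comparison between operations is kept, change the test named in the lung-function item of section 10.2 to Welch's unequal-variance t-test with its 95% confidence interval.

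The cost is one phrase and, if the SDs are in truth equal, some power: about 75% instead of 79% at 40 v 10 for a 1-SD difference. At very small group sizes Welch is itself slightly above nominal (up to 5.8% at 45 v 5).

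The change leaves open who the two groups are and how far a non-randomised comparison between them can be interpreted. The protocol has to settle that separately.
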